### **9.3.2 Adverse Reaction and Suspected Adverse Reaction**

An adverse reaction is any AE caused by the Study Drug.

A suspected adverse reaction is any AE for which there is a reasonable possibility that the drug caused the adverse event. A suspected adverse reaction implies a lesser degree of certainty about causality than an adverse reaction.

### **9.3.3 Serious Adverse Event (SAE)**

A serious adverse event is any adverse event that in the view of either the Investigator or Sponsor, meets any of the following criteria:

- Results in death
- Is life threatening: that is, poses an immediate risk of death at the time of the event  
An AE or suspected adverse reaction is considered “life-threatening” if, in the view of either the Investigator or Sponsor, its occurrence places the subject at immediate risk of death. It does not include an AE or suspected adverse reaction that, had it occurred in a more severe form, might have caused death
- Requires inpatient hospitalization or prolongation of existing hospitalization  
Hospitalization is defined as an admission of greater than 24 hours to a medical facility and does not always qualify as an AE
- Results in a persistent or significant incapacity or substantial disruption of the ability to conduct normal life functions
- Results in a congenital anomaly or birth defect in the offspring of the subject (whether the subject is male or female)
- Important medical events that may not result in death, are not life-threatening, or do not require hospitalization may also be considered serious when, based upon appropriate medical judgment, they may jeopardize the subject and may require medical or surgical intervention to prevent one of the outcomes listed in this definition. Examples of such medical events include allergic bronchospasm requiring intensive treatment in an emergency room or at home, blood dyscrasias or convulsions that do not result in inpatient hospitalization, or the development of drug dependency or drug abuse

## **9.4 Monitoring and Recording of Adverse Events**

Any pre-existing conditions or signs and/or symptoms present in a subject prior to the start of the study (i.e., before informed consent) should be recorded as Medical History and not recorded as AEs unless the pre-existing condition worsened. The Investigator should always group signs and symptoms into a single term that constitutes a **single unifying diagnosis** if possible.

### **9.4.1 Serious Adverse Events**

In the interest of subject safety, and in order to fulfill regulatory requirements, all SAEs (regardless of their relationship to Study Drug) should be reported to the Sponsor or designee within 24 hours of the Study Center’s first knowledge of the event. The collection of SAEs will

begin after the subject signs the informed consent form and stop at the end of the subject's follow-up period. An Initial Serious Adverse Event Form should be completed and a copy should be faxed to the Sponsor or designee.

The contact information for reporting SAEs is as follows:

**Attention:** [REDACTED]

**Email:** [REDACTED]

**Fax:** [REDACTED]

Detailed information should be actively sought and included on Follow-Up Serious Adverse Event Forms as soon as additional information becomes available. All SAEs will be followed until resolution. SAEs that remain ongoing past the subject's last protocol-specified follow-up visit will be evaluated by the Investigator and Sponsor. If the Investigator and Sponsor agree the subject's condition is unlikely to resolve, the Investigator and Sponsor will determine the follow-up requirement.

#### **9.4.2 Non-Serious Adverse Events**

The recording of non-serious AEs will begin after the subject signs the informed consent form and will stop at the end of the subject's follow-up period. The Investigator will monitor each subject closely and record all observed or volunteered AEs on the Adverse Event Case Report Form.

#### **9.4.3 Evaluation of Adverse Events (Serious and Non-Serious)**

The Investigator's opinion of the following should be documented on the Adverse Event Case Report Form.

##### **9.4.3.1 Relationship to the Study Drug**

The event's relationship to the Study Drug (ISIS 703802 or placebo) is characterized by one of the following:

- **Related:** There is clear evidence that the event is related to the use of Study Drug, e.g., confirmation by positive re-challenge test
- **Possible:** The event cannot be explained by the subject's medical condition, concomitant therapy, or other causes, and there is a plausible temporal relationship between the event and Study Drug (ISIS 703802 or placebo) administration
- **Unlikely/Remote:** An event for which an alternative explanation is more likely (e.g., concomitant medications or ongoing medical conditions) or the temporal relationship to Study Drug (ISIS 703802 or placebo) administration and/or exposure suggests that a causal relationship is unlikely (For reporting purposes, Unlikely/Remote will be grouped together with Not Related)

- **Not Related:** The event can be readily explained by the subject's underlying medical condition, concomitant therapy, or other causes, and therefore, the Investigator believes no relationship exists between the event and Study Drug

#### 9.4.3.2 *Severity*

The severity of AEs and SAEs will be graded based on criteria from the Common Terminology Criteria for Adverse Events (CTCAE) Version 4.03, June 2010 (refer to [Appendix D](#)). Any AE not listed in [Appendix D](#) will be graded as follows:

- **Mild:** The event is easily tolerated by the subject and does not affect the subject's usual daily activities
- **Moderate:** The event causes the subject more discomfort and interrupts the subject's usual daily activities
- **Severe:** The event is incapacitating and causes considerable interference with the subject's usual daily activities

If the event is an SAE, then all applicable seriousness criteria must be indicated (criteria listed in [Section 9.3.3](#)).

#### 9.4.3.3 *Action Taken with Study Drug*

Action taken with Study Drug (ISIS 703802 or placebo) due to the event is characterized by one of the following.

- **None:** No changes were made to Study Drug (ISIS 703802 or placebo) administration and dose
- **Permanently Discontinued:** Study drug was discontinued and not restarted
- **Temporarily Interrupted, Restarted – Same Dose:** Dosing was temporarily interrupted or delayed due to the AE and restarted at the same dose
- **Temporarily Interrupted, Restarted – Reduced Dose:** Dosing was temporarily interrupted or delayed due to the AE and restarted at the next lower dose

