**Table 3 Actions in Subjects with Low Platelet Count**

Platelet Count on Rx	Drug Dose	Monitoring
Normal range, $\geq 140\text{K}/\text{mm}^3$	No action	Monitor every 14 days (+/- 2 days)
$\geq 100\text{K}$ to $<140\text{K}/\text{mm}^3$	No action	Closer observation Monitor every week*
$\geq 75\text{K}$ to $<100\text{K}/\text{mm}^3$	Permanently reduce the dose by 50 % as follows: For Cohort A: reduce to 10 mg every week For Cohort B: reduce to 20 mg every 4 weeks For Cohort C: reduce to 40 mg every 4 weeks	Closer observation Monitor every week*
$\geq 50\text{K}$ to $<75\text{K}/\text{mm}^3$	Pause dosing When platelet count returns to $> 100\text{K}/\text{mm}^3$ restart dosing as follows only if approved by Sponsor Medical Monitor: For Cohort A: reduce to 10 mg every week For Cohort B: reduce to 20 mg every 4 weeks For Cohort C: reduce to 40 mg every 4 weeks  or Permanently discontinue Study Drug if it occurs while on already reduced dose	Closer observation Monitor every 2-3 days until 2 successive values show improvement Consider discontinuation of antiplatelet agents/non-steroidal anti-inflammatory drug (NSAIDS)/ anticoagulant medication
$\geq 25\text{K}$ to $<50\text{K}/\text{mm}^3$	Permanently discontinue Study Drug	Closer observation: Monitor daily until 2 successive values show improvement then monitor every 2-3 days until platelet count stable Discontinue antiplatelet agents/NSAIDS/anticoagulant medication while platelet count $< 50\text{K}/\text{mm}^3$ if possible Refer to hematologist to provide diagnostic and therapeutic management
$< 25\text{K}/\text{mm}^3$	Permanently discontinue Study Drug	Closer observation: Monitor daily until 2 successive values show improvement then monitor every 2-3 days until platelet count stable Steroids recommended** Consider need for hospitalization Discontinue antiplatelet agents/NSAIDS/anticoagulant medication while platelet count $< 50\text{K}/\text{mm}^3$ if possible Refer to hematologist to provide diagnostic and therapeutic management

\* Once a subject commences weekly monitoring this frequency of monitoring should continue until the platelet count returns to the normal range ( $\geq 140,000/\text{mm}^3$ ) for 2 successive values.

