Unless otherwise specified, the frequency of patients with any incidence of AEs and the number of events will be summarized by system organ class (SOC) and MedDRA preferred term (PT) for:

- TEAE
- TEAEs potentially related to Study Drug. Related is defined as “Related”, “Possible”, or missing relationship to Study Drug
- TEAEs by SOC, PT and severity. At each level of patient summarization, a patient with multiple events is counted only once according to the worst reported severity. Adverse events with missing severity will be categorized as “Missing” for this summary.
- TEAEs potentially related to Study Drug by severity
- Most common TEAEs by PT. Most common TEAEs are defined as an incidence of 10% or more within any treatment groups at preferred term level.
- Treatment-emergent serious adverse events (SAEs)
- Treatment-emergent SAEs potentially related to Study Drug
- TEAEs leading to permanent treatment discontinuation
- TEAEs leading to death.

Summary tables will be sorted by decreasing frequency of SOC and then by decreasing frequency of PT within SOC in Pooled ISIS 703802 column. If frequency is same for different PTs, sort alphabetically. If SOC or PT is missing, show as “Not Coded” in table.

An overview of AEs will be provided for all TEAEs. Treatment-emergent AEs, treatment-emergent SAEs, TEAEs potentially related to Study Drug, TEAEs that lead to treatment discontinuation, treatment interruption, dose reduction, and death. Original CRF collected dates will be used for listings.

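### The adverse-event 'action taken' list has no code for a dose reduced without interruption, so the SAP's dose-reduction and interruption rows may be misclassified

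*Protocol*

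**What the plan says.** Protocol 9.4.3.3 says that the action taken with study drug "due to the event is characterized by one of the following". It then defines four codes:

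- None: "No changes were made to Study Drug (ISIS 703802 or placebo) administration and dose".
- Permanently Discontinued: "Study drug was discontinued and not restarted".
- Interrupted, restarted at the same dose: "Dosing was temporarily interrupted or delayed due to the AE and restarted at the same dose".
- Interrupted, restarted at a reduced dose: "Dosing was temporarily interrupted or delayed due to the AE and restarted at the next lower dose".

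Section 9.4.3 directs that these items be recorded on the adverse event case report form.

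Protocol Table 3 treats two platelet bands differently. From 75,000 to below 100,000/mm³ the instruction is "Permanently reduce the dose by 50 % as follows", and the row contains no pause. From 50,000 to below 75,000/mm³ the drug is paused first; after recovery, and only with the medical monitor's approval, the site may "restart dosing as follows", at the reduced dose. Section 8.7 makes Table 3 binding for platelet-related changes. For other safety or tolerability reasons it names interruption and dose decrease as separate options, joined by and/or.

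The adverse-event overview in SAP 3.5.1 covers "TEAEs that lead to treatment discontinuation, treatment interruption, dose reduction, and death". It does not name the field or derivation that supplies the interruption and reduction rows.

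**The concern.** The protocol distinguishes reducing the dose from pausing and then restarting at a lower dose, but its code list recognises only the second. A site that halves the next scheduled dose on time, because of an adverse event, has no accurate code to choose. The SAP then reports interruption and reduction as separate items. What is at stake is how accurately that overview shows how often each regimen had to be reduced or interrupted because of an adverse event. That is a tolerability comparison between weekly and 4-weekly dosing in a dose-finding trial.

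**Working it through.** The plan states no expected number of dose reductions, so there is no figure of its own to reproduce. The check is a comparison of the texts, followed by a calculation of scale.

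**1. Does a reduction without a pause fit any code?** Take an adverse event after which the next dose is given on schedule at half strength.

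| Code in 9.4.3.3 | What it requires | Met? |
|---|---|---|
| None | administration and dose both unchanged | No, the dose changed |
| Permanently Discontinued | drug stopped for good | No |
| Interrupted, same dose | a pause or delay, then the same dose | No |
| Interrupted, reduced dose | a pause or delay, then a lower dose | No, there was no pause or delay |

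The list is worded as closed, so one of these must be used.

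**2. Effect on the SAP rows, per event, if the rows are built from this field.**

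| Code chosen | Dose-reduction row | Interruption row |
|---|---|---|
| None | 1 too low | correct |
| Interrupted, reduced dose | correct | 1 too high |

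Each event therefore distorts one row, not both. In a count of subjects the effect is at most one per subject, and it is nil if another event already places that subject in the row correctly.

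**3. Does confirmatory testing create a delay anyway?** Protocol 8.5 requires a new specimen before the next dose, ideally within 3 days of the initial collection. Section 6.2 expects lab alerts within 2 days of collection and allows the investigator 48 hours from receipt to review.

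- Days from initial sample to reviewed retest: 3 + 2 + 2 = 7.
- Slack with weekly dosing, if the first sample is drawn on a dosing day: 7 − 7 = 0 days.
- Slack with 4-weekly dosing, on the same assumption: 28 − 7 = 21 days.

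Some weekly doses may be delayed, and the fourth code would then be accurate. A 4-weekly dose need not be. The gap could therefore affect the regimens unequally, although the documents do not show that it will.

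**4. Scale.** One subject in an arm of 24 is 1/24 = 4.2 percentage points. The chance of at least one affected subject is 1 − (1 − p)^n. The documents give no value for p, so the non-zero rates below are assumptions.

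| Assumed rate p per subject | n = 96 (all randomized) | n = 72 (active only) |
|---|---|---|
| 0 | 0% | 0% |
| 0.5% | 38.2% | 30.3% |
| 1% | 61.9% | 51.5% |
| 2% | 85.6% | 76.7% |
| 5% | 99.3% | 97.5% |

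The number of misclassified events equals the number of adverse events managed by reduction without a pause, and that may be zero.

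**The case against.** The strongest reply is that nothing here shows any count to be wrong. Misclassification needs four things: such a reduction occurs; its trigger is reported as an adverse event; the eCRF offers only these four options; and the SAP rows come from that field alone. The SAP is based on eCRF Version 10, which is not among the documents, and SAP 3.5.1 names no source field. Protocol 9.5.1 keeps laboratory findings judged not clinically significant out of adverse-event reporting, so some Table 3 reductions will have no adverse-event record and no extra code would capture them. Phase 1 reported no significant falls in platelet count with this drug. All of this stands, and it limits the point to possible misclassification.

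A reader might infer that both rows must be wrong for every reduction of this kind. The documents do not support that. Each event affects one row, a dose delayed by retesting fits the fourth code, and the form cannot be seen.

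A reader might also infer that the platelet evidence for dose selection is compromised. It is not. SAP 3.5.2 tabulates counts below 100,000/mm³, nadir bands that include 75,000 to below 100,000/mm³, falls of at least 30% and 50% from baseline, and patients meeting the monitoring and stopping rules. SAP 3.2.7 summarizes the amount of drug received and compliance. None of these is defined from the action code.

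The reply does not remove the gap. The protocol's own list, followed as written, gives no correct entry for an action that the protocol mandates. Section 9.5.3 says that dosing details go on the Dosing eCRF, but nothing described there ties a dose change to a particular adverse event.

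**Conclusion.** The gap in 9.4.3.3 is established from the text: no code covers a dose reduced without interruption or delay, Table 3 mandates that action in one platelet band, and section 8.7 allows it elsewhere. The consequence is conditional. If the eCRF copies the list and the overview rows are taken from it, each adverse event of this kind puts one row out by one event. The number of such events is unknown and may be zero. The effect is confined to descriptive rows of the adverse-event overview; it does not reach the primary endpoint, any hypothesis test or the laboratory platelet summaries. It is still worth correcting, because the instruction is incomplete for an action that the protocol requires and the repair is cheap.

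**What to change.** 1. Check the action-taken options in eCRF Version 10. If a reduction without interruption is absent, add a code such as 'Dose reduced, not interrupted' to protocol 9.4.3.3 and to the adverse event form. If the form already has it, only the protocol list needs aligning.
2. In SAP 3.5.1, define the dose-reduction row as the new code plus the interrupted-and-restarted-at-reduced-dose code. Define the interruption row as the two interruption codes only.
3. For entries already made, compare adverse-event records with dose and dates on the Dosing eCRF, and query the site where they disagree. Do this before the end-of-treatment lock and unblinding. The dosing record can show that a dose changed, but the site must say which event caused it, so recoding from that form alone is not enough.

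The cost is one protocol bullet, one form option if needed, a sentence or two in the SAP and a small amount of query work. No dosing or stopping rule changes.

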#### 9.4.3.4 *Treatment Given for Adverse Event*

Any treatment (e.g., medications or procedures) given for the AE should be recorded on the Adverse Event Case Report Form. Treatment should also be recorded on the concomitant treatment or ancillary procedures eCRF, as appropriate.

#### 9.4.3.5 *Outcome of the Adverse Event*

If the event is a non-serious AE, then the event's outcome is characterized by one of the following:

- **AE Persists:** Subject terminates from the trial and the AE continues
- **Recovered:** Subject recovered completely from the AE

- **Became Serious:** The event became serious (the date that the event became serious should be recorded as the Resolution Date of that AE and the Onset Date of the corresponding SAE)
- **Change in Severity (if applicable):** AE severity changed

If the event is an SAE, then the event's outcome is characterized by one of the following:

- **Ongoing:** SAE continuing
- **Persists (as non-serious AE):** Subject has not fully recovered but the event no longer meets serious criteria and should be captured as an AE on the non-serious AE eCRF (the SAE resolution date should be entered as the date of onset of that AE)
- **Recovered:** Subject recovered completely from the SAE (the date of recovery should be entered as the SAE resolution date)
- **Fatal:** Subject died (the date of death should be entered as the SAE resolution date)

## 9.5 Procedures for Handling Special Situations

### 9.5.1 *Abnormalities of Laboratory Tests*

Clinically significant abnormal laboratory test results may, in the opinion of the Investigator, constitute or be associated with an AE. Examples of these include abnormal laboratory results that are associated with symptoms, or require treatment, e.g., bleeding due to thrombocytopenia, tetany due to hypocalcemia, or cardiac arrhythmias due to hyperkalemia. Whenever possible, the underlying diagnosis should be listed in preference to abnormal laboratory values as AEs. Clinically significant abnormalities will be monitored by the Investigator until the parameter returns to its Baseline value or until agreement is reached between the Investigator and Sponsor Medical Monitor. Laboratory abnormalities deemed not clinically significant (NCS) by the Investigator should not be reported as AEs. Similarly, laboratory abnormalities reported as AEs by the Investigator should not be deemed NCS on the laboratory sheet.

The Investigator is responsible for reviewing and signing all laboratory reports. The signed clinical laboratory reports will serve as source documents and should include the Investigator's assessment of clinical significance of out of range/abnormal laboratory values.

### 9.5.2 *Prescheduled or Elective Procedures or Routinely Scheduled Treatments*

A prescheduled or elective procedure or a routinely scheduled treatment will not be considered an SAE, even if the subject is hospitalized; the Study Center must document all of the following:

- The prescheduled or elective procedure or routinely scheduled treatment was scheduled (or was on a waiting list to be scheduled) prior to obtaining the subject's consent to participate in the study
- The condition that required the prescheduled or elective procedure or routinely scheduled treatment was present before and did not worsen or progress in the opinion of the Investigator between the subject's consent to participate in the study and the timing of the procedure or treatment

- The prescheduled or elective procedure or routinely scheduled treatment is the sole reason for the intervention or hospital admission

### 9.5.3 *Dosing Errors*

Study Drug (ISIS 703802 or placebo) errors should be documented as Protocol Deviations. A brief description should be provided in the deviation, including whether the subject was symptomatic (list symptoms) or asymptomatic, and the event accidental or intentional.

Dosing details should be captured on the Dosing eCRF. If the subject takes a dose of Study Drug (ISIS 703802 or placebo) that exceeds protocol specifications and the subject is symptomatic, then the symptom(s) should be documented as an AE and be reported per [Section 9.4](#).

**Should an overdose occur**, the Investigator or designee should refer to the Guidance to Investigators section of the Investigator's Brochure and contact the Sponsor or designee within 24 hours.

### 9.5.4 *Contraception and Pregnancy*

Subjects must continue to use appropriate contraception with their partners, or refrain from sexual activity, as described in [Section 6.3.1](#).

If a subject becomes pregnant or a pregnancy is suspected, or if a male subject makes or believes that he has made someone pregnant during the study, then the Study Center staff must be informed immediately. An Initial Pregnancy Form should be submitted to the Sponsor or designee **within 24 hours** of first learning of the occurrence of pregnancy. Follow-up information including delivery or termination is reported by designating as 'Follow-up' on the Pregnancy Forms and reported within 24 hours.

Payment for all aspects of obstetrical care, child or related care will be the subject's responsibility.

Female subjects: If a suspected pregnancy occurs while on the study (including follow-up), a pregnancy test will be performed. The subject with a confirmed pregnancy will be immediately withdrawn from treatment with Study Drug. However, the subject will be encouraged to complete the post-treatment follow-up portion of the study to the extent that study procedures do not interfere with the pregnancy. Regardless of continued study participation, the study physician will assist the subject in getting obstetrical care and the progress of the pregnancy will be followed until the outcome of the pregnancy is known (i.e., delivery, elective termination, or spontaneous abortion). If the pregnancy results in the birth of a child, the Study Center and Sponsor may require access to the mother and infant's medical records for an additional 8 weeks after birth. Follow-up will be performed to the extent permitted by the applicable regulations and privacy considerations.

Male subjects: The progress of the pregnancy of a male subject's partner should be followed until the outcome of the pregnancy is known (i.e., delivery, elective termination, or spontaneous abortion). If the pregnancy results in the birth of a child, **the Study Center and Sponsor may request access to the mother and infant's medical records for an additional 8 weeks after**

**birth.** Follow-up will be performed to the extent permitted by the applicable regulations and privacy considerations.

